| RATIONALE AND BACKGROUND | 
Due to the rarity of mycosis fungoides cutaneous T-cell lymphoma (MF-CTCL), there is a dearth of epidemiologic data detailing the clinical course of the disease and its response to treatment. While topical treatment with mechlorethamine hydrochloride (MCH) has been used since the 1950s, prospective data describing the clinical course of MF-CTCL is limited. Valchlor gel is a new formulation of MCH (or nitrogen mustard) that has been shown to be safe and effective in a clinical trial and has been approved for Stage I MF-CTCL patients
 
Prospective data on Valchlor are currently only available from the pivotal, randomized, controlled clinical trial with strict inclusion and exclusion criteria. Understanding real-world patient safety and tolerability, as well as compliance and discontinuation rates, will assist with the management of Valchlor-treated MF-CTCL patients. This study will build and extend on the data from the Valchlor clinical development program, increase the understanding of the use of Valchlor in patients with MF-CTCL and, while limited to patients treated with Valchlor, will represent the largest prospective study with any given MF-CTCL treatment.
 
This large, non-interventional study will provide information on the use of Valchlor in a ‘real-world’ clinical practice setting, and increase understanding of the management and outcomes of Valchlor-treated MF-CTCL patients. Data collected includes, but is not limited to: outcomes (e.g., clinical status and healthcare utilization [MF-CTCL-related hospitalizations and emergency room visits]), adverse events (AEs; e.g., dermatitis), clinical characteristics, and treatment patterns. Finally, this study will document disease burden (e.g., pruritus) of MF-CTCL in a real-life
 |

| | |
|----------------------------------|--|
| | 
setting by collecting patient-completed symptoms and quality of life (QOL) questionnaires for patients with skin disease. The QOL tools include VAS, Skindex-29 and a newly validated Mycosis fungoides / Sézary syndrome-type cutaneous T-cell lymphoma (MF/SS-CTCL) questionnaires.
 |
| RESEARCH QUESTION AND OBJECTIVES | 
The objectives of this study are:
 
• To describe clinical characteristics of patients treated with Valchlor at enrollment and during the study observation period.• To describe treatment and response assessment patterns of patients with MF-CTCL treated with Valchlor at enrollment and during the study observation period.• To assess outcomes (e.g., clinical status and rates of healthcare utilization [MF-CTCL-related hospitalizations and emergency room visits]) in patients with MF-CTCL treated with Valchlor during the study observation period.• To collect and describe the incidence of AEs/serious adverse events (SAEs) in patients with MF-CTCL treated with Valchlor:
○ To estimate the incidence of dermatitis in patients using Valchlor during the study observation period.○ To describe the management of dermatitis in patients using Valchlor at enrollment and during the study observation period.• To collect patient-completed symptoms and QOL questionnaires. |
| STUDY DESIGN | 
This is a multi-center, prospective, observational, US-based drug study.
 
All consecutive MF-CTCL patients being treated with Valchlor will be invited to enroll in this study.
 
Patients will undergo clinical assessments and receive standard medical care, as determined by the patients' physician, in the real-world setting. With the exception of protocol-required patient-completed questionnaires for symptoms and QOL, there are no specific or mandated clinical assessments to be performed, and patients will not receive experimental intervention or treatment as a consequence of their participation in this study.
 
Patients will be followed prospectively for a maximum of 2 years
 |

| | |
|--|---|
| | 
from the date of signed informed consent (enrollment) until end of study, which includes withdrawal of consent, loss to follow-up, death, or study completion. Continuation in the study is not contingent on continuation of Valchlor.
 
Patients currently enrolled and ongoing or newly enrolled will be offered to participate in the 24-month study of this protocol Amendment 1. Patients who enrolled under the original protocol (prior to Amendment 1) and are still ongoing in the study will be re-consented and to follow data collection specified in Table 1 of this protocol for a total of 24 months from original consent date. Patients who enrolled and have completed 1 year of the study under the original protocol will not be re-consented under Amendment 1.
 |
| 
POPULATION (SETTING AND STUDY POPULATION)
 | 
This study will enroll approximately 300 consecutive patients diagnosed with MF-CTCL and being treated with Valchlor, regardless of other MF-CTCL therapies received before or at enrollment. Patients will be enrolled from up to 50 participating centers/clinics in university-affiliated or community hospitals in the US. The participation of physicians and patients in the study is on a voluntary basis.
 
Inclusion criteria:
 
 • All adult patients (≥ 18 years of age) diagnosed with MF-CTCL and being treated with Valchlor. This includes patients newly initiating Valchlor OR patients continuing treatment with Valchlor: 
 ○ Patients newly initiating Valchlor are patients who have their first office visit after having initiated Valchlor. ○ Patients continuing treatment with Valchlor includes patients who are actively taking Valchlor on the day of enrollment. ○ Signed patient informed consent. 
Exclusion criteria:
 
 • None |
| 
VARIABLES
 | 
The variables of interest for this study includes clinical characteristics, treatment patterns, clinical status, as assessed by the physician (including the methods used in practice to assess clinical status), MF-CTCL-related healthcare utilization, as assessed by the physician (hospitalizations and emergency room visits), AEs and
 |

| | |
|--|---|
| | 
SAEs, patient-completed symptoms and QOL questionnaires.
 
Due to expected variability in practice patterns, no individual method of determining response is mandated, but assessments that do occur must be captured prospectively. Additionally, it is important to capture which methods were used pre-study, even where results may not be available, so that it is clear which assessments have a prior assessment that may have been considered in the physician's evaluation of response.
 
The specific outcomes and variables of interest for the study are:
 
Clinical characteristics.
 
Relevant medical history, including tumor-node-metastasis-blood (TNMB) classification.
 
Use of prior MF-CTCL treatments.
 
Treatment patterns, including prescribing information, for the treatment of MF-CTCL (including dosing regimens, titration schemes, duration of time from initiation to discontinuation of therapy, and drug holidays for Valchlor).
 
Clinical status, as assessed by the physician (i.e., complete response, partial response, stable disease, progressive disease, relapse).
 
Assessments (both whether or not the assessment was performed and the result of the assessment) used to define response, including, but not limited to:
 
○ Composite Assessment of Index Lesion Severity (CAILS).○ Modified Severity Weighted Assessment Tool (mSWAT).○ Physician's Global Assessment.○ Body Surface Area (BSA) of disease. 
Healthcare utilization related to MF-CTCL during the study period, as assessed by physician:
 
○ Number of MF-CTCL-related hospitalizations.○ Number of MF-CTCL-related emergency room visits. 
AEs and SAEs (e.g., dermatitis) whether or not related to Valchlor.
 |
|--|---|

| | |
|--------------|--|
| | 
Patient-completed questionnaires:
 
○ Visual Analogue Scale (VAS) for pruritus (scale 0–10).○ Skindex-29.○ MF/SS CTCL. |
| DATA SOURCES | 
Information will be collected per routine clinical practice. No specific clinical mandated assessments are to be performed as part of study participation. Patient-completed questionnaires, however, are a study requirement and will be collected at all clinic visits during the study observation period. These questionnaires will be administered on paper by study coordinators. Patient clinical data (non-patient-completed) will be collected from the patient's medical records at enrollment and throughout the study period. All data will be entered into electronic Case Report Forms (eCRFs) at the time of collection or on a quarterly basis by study coordinators. AEs and SAEs whether or not related to Valchlor will be entered into the eCRF at every visit and upon notification by the patient (e.g., reported via phone call).
 
For patients who do not have any visits, an affirmative response that the patient is still under care by the site will be requested quarterly, so that the absence of reported assessments can be interpreted the same as the actual absence of actual assessments.
 
Pre-treatment information will be collected at the time of enrollment using the following variables:
 
● Weight● TNMB classification● Use of Valchlor and other MF-CTCL treatments● Assessments used to define response (whether or not the assessment was ever performed, and regardless of whether the assessment was used to assess response for a previously treated patient or whether the assessment was performed for a comparison with future evaluations of response, and the results of the most recent assessments), including, but not limited to:
○ CAILS.○ mSWAT.○ Physician's Global Assessment.○ BSA of disease. 
In addition, the following information will be collected at the time
 |

| | |
|--|---|
| | 
of enrollment:
 
Patient demographics.
 
Relevant medical history
 
MF-CTCL TNMB classification.
 
MF-CTCL histology.
 
Use of Valchlor and other MF-CTCL treatments (including start and stop dates for each medication, and reasons for starting and stopping medications).
 
Clinical status, as assessed by the physician (i.e., complete response, partial response, stable disease, progressive disease, relapse).
 
Assessments (both whether or not the assessment was performed and the result of the assessment) used to assess response, including, but not limited to:
 
○ CAILS.○ mSWAT.○ Physician’s Global Assessment.○ BSA of disease. 
All ongoing AEs and SAEs.
 
Patient-completed questionnaires:
 
○ VAS for pruritus (scale 0–10).○ Skindex-29.○ MF/SS CTCL 
The following information will be collected at all clinic visits occurring during the observation period:
 
MF-CTCL TNMB classification changes.
 
Changes in relevant medical history.
 
Use of Valchlor and other MF-CTCL treatments (including start and stop dates for each medication, and reasons for starting and stopping medications).
 
Healthcare utilization related to MF-CTCL since the last study visit, as assessed by physician:
 
○ Number of MF-CTCL-related hospitalizations |
|--|---|

| | |
|------------|--|
| | 
(including length of stay and primary admission and discharge diagnoses).
 
 ○ Number of MF-CTCL-related emergency room visits. 
Clinical status, as assessed by physician (i.e., complete response, partial response, stable disease, progressive disease, relapse).
 
Assessments (whether or not the assessment was performed and the result of the assessment) used to assess response, including, but not limited to:
 
 ○ CAILS. ○ mSWAT. ○ Physician’s Global Assessment. ○ BSA of disease. 
All AEs and SAEs (e.g., dermatitis) whether or not related to Valchlor, including reports of secondary exposures since last visit (while on Valchlor only).
 
Patient-completed questionnaires:
 
 ○ VAS for pruritus (scale 0–10). ○ Skindex-29. ○ MF/SS-CTCL. 
Patients who enrolled under the original protocol and are still ongoing in the study will be contacted and informed consent will be obtained for the Amendment 1 protocol. Patients prospective data will be collected up to a total of 24 months from the original enrollment date.
 |
| STUDY SIZE | 
This study will enroll approximately 300 patients diagnosed with MF-CTCL who are being treated with Valchlor.
 
A sample size of 270 evaluable patients is needed to estimate the percentage of patients with clinical status and the rate of hospitalizations, both with a margin of error of 6 percentage points. Assuming that up to 10% of patients may be non-evaluable due to incomplete follow-up, the sample size target for enrollment should be 300. It is projected that approximately 200 evaluable patients currently enrolled will be re-consented and newly enrolled will be consented under Amendment 1 for a 2-year follow-up. The margin of error for 200 evaluable patients will be 7%.
 
Additionally, it is important to be able to estimate these same
 |

| | |
|----------------------|---|
| | 
percentages with a margin of error of 10 percentage points or less for key subgroups representing a third or more of the patient population (e.g., patients newly initiating Valchlor). A total of 100 patients are required to achieve a margin of error of 10 percentage points, so that a total enrollment of 300 patients is needed.
 |
| 
DATA ANALYSIS
 | 
Demographics and clinical characteristics will be summarized for all patients enrolled as well as grouped separately for patients continuing treatment with Valchlor versus patients who are newly initiating Valchlor. Use of prior treatments and past methods of assessing response will similarly be analyzed separately for the two groups. Treatments individually and in combination will be reported in percentage terms, by visit, stratified by newly initiating patients and continuing patients to identify treatment patterns.
 
Analyses of response, based on a particular measure of response, will be limited to patients for whom that measure was reported. Therefore, patients with reported data will be summarized also for patients without any reported data with respect to demographics and pre-treatment clinical status to identify potential biases. Rates of on-study hospitalization and emergency room visits will be computed as the utilization counts divided by on-study days. The summary of response rates will be tabulated and the definition of response will be detailed in the Statistical Analysis Plan.
 
The frequency and percentage of patients experiencing any AEs or SAEs will be summarized by system organ class and preferred MedDRA terminology. SAEs requiring hospitalizations and fatal SAEs will be displayed in patient listings.
 
At each visit performed during the observation period (1st, 2nd, etc.), the VAS for pruritus, the three scales of the Skindex-29 and the MF/SS-CTCL questionnaires will be computed for patients who are and are not responders. These descriptive cross-sectional comparisons are intended to assess burden of disease in a Valchlor-treated cohort over time.
 |
| 
MILESTONES
 | 
First patient, first visit: Q4 2014
 
Last patient, first visit: Q3 2017
 
Last patient, last visit: Q3 2019
 |

| | |
|--------------------|---|
| DATA OWNERSHIP | Actelion Pharmaceuticals US, Inc. |
| STUDY COMMITTEE(S) | The Scientific Committee will consist of 4–6 key opinion leaders in the field of MF-CTCL who will provide scientific input on the MF-CTCL Study protocol and review study data. |

PROTOCOL

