| Healthcare utilization related to MF-CTCL (as assessed by physician) | | |
| Hospital admissions [‡] | | X |
| Emergency room visits | | X |
| Clinical Status (as assessed by physician) | X | X |
| Clinical Status Assessments* | | |
| Composite Assessment of Index Lesion Severity | X | X |
| Modified Severity Weighted Assessment Tool | X | X |
| Physician's Global Assessment | X | X |
| Body Surface Area of disease | X | X |
| Patient-Completed Questionnaires[§] | | |
| Visual Analogue Scale for pruritus | X | X |
| Skindex-29 | X | X |
| Mycosis fungoides / Sézary syndrome-type cutaneous T-cell lymphoma | X | X |
| Safety Measures^{**} | | |
| AEs and SAEs | X ⁺ | X |
| Reports of secondary exposures | | X [^] |

*Included in pre-treatment data collection, which is performed at enrollment. All data must be completed as available.

[†]Includes collection of start and stop dates for each medication, including reasons for starting and stopping medications. Start and stop dates are also collected for Valchlor, including short gaps in treatment, such as drug holidays.

[‡]For each hospital admission, length of stay and primary admission and discharge diagnoses will be collected.

[§]To be completed by patients who can read and understand English and are able to self-complete the questionnaires based on the investigator's assessment. Patients who are unable to self-complete the questionnaires will not be excluded from the study.

^{**}Safety measures, which include AEs and SAEs, will be collected from the informed consent date and prospectively at every visit during the study and up to 30-days post-discontinuation of Valchlor during the study. Ongoing AE and SAE data will be collected through the end of study, regardless of Valchlor use.

New AEs and SAEs that occur more than 30 days after discontinuation of Valchlor will be reported to Actelion US Drug Safety if investigator feels there is a possible causal relationship with Valchlor. Investigators are also expected to assess patients for AEs and SAEs and follow the appropriate reporting procedures per Section 7.

⁺All ongoing AEs and SAEs for patients being treated [see Section 5.2.1 for definition of “being treated”] with Valchlor.

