5.3.2 Exposure definition and measures

Start of observation is defined as date of signed informed consent.

End of observation is defined as EOS, including death, withdrawal of consent, loss to follow-up, or study completion, whichever occurs first.

Total exposure time is defined as the date of first Valchlor exposure to the date of last Valchlor exposure.

Total on-study Valchlor exposure time is defined as the first day of Valchlor use to last day of Valchlor use during the observation period. If the patient was using Valchlor at end of observation, the last on-study day of Valchlor use is equal to the end date of observation period. Drug holidays are excluded from the sum of exposure time.

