5.7.5 Adverse events

The frequency and percentage of patients experiencing any on-study AEs, SAEs, or death will be summarized by system organ class and preferred MedDRA terminology. Additional detail for AEs of special interest (e.g., dermatitis) will be summarized separately. SAEs will be displayed in patient listings, both including and excluding events that were not concurrent with Valchlor exposure. The definition of an on-study event is one that occurs on the day of enrollment or later, but before the date of study discontinuation or completion.

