**Skindex-29, Functioning**

Baseline Completed [(mean +/- SD) (min, max)]	n= xx.x +/- xx.x (xx,xx)				
Baseline Not Done [(mean +/- SD) (min, max)]					

Follow-Up Completed	n=	n=	n=	n=	n=
---------------------	----	----	----	----	----

Quarter 1 [(mean +/- SD) (min, max)]	xx.x +/- xx.x (xx,xx)				
Quarter 2 [(mean +/- SD) (min, max)]					
Quarter 3 [(mean +/- SD) (min, max)]					
Quarter 4 [(mean +/- SD) (min, max)]					
Follow-Up Not Done [(mean +/- SD) (min, max)]					

- 
- a. Patients can contribute multiple visits to a quarter. These visits could be categorized as response or non-response for the same patient within a quarter.

Run Date: ddMMMyyyy

Date of Data Extraction: ddMMMyyyy

Helsinn Therapeutics (US),  
 Inc., Protocol AC-079A501  
 (PROVe)

Table 18. Adverse Events

Characteristic	V+C+ Other	V+P+ Other	V+OB+ Other	V+ Other
	n=		n=	n=
Overall a	xx (xx.x)		xx (xx.x)	xx (xx.x)
System Organ Class 1				
Preferred Term A				
Preferred Term B	xx.x +/- xx.x		xx.x +/- xx.x	xx.x +/- xx.x
...				
System Organ Class 2				
Preferred Term C	xx (xx.x)		xx (xx.x)	xx (xx.x)
...				
...				

---

Note: Number of subjects and % of subjects are shown

a. Overall refers to any recorded AE, including AEs reported as ongoing at the time of enrollment

Run Date: ddMMMyyyy

Date of Data Extraction: ddMMMyyyy

Helsinn Therapeutics (US), Inc.,  
 Protocol AC-079A501 (PROVe)  
 Table 19. Serious Adverse Events

Characteristic	V+C+ Other	V+P+ Other	V+OB+ Other	V+ Other
	n= xx (xx.x)	n= xx (xx.x)	n= xx (xx.x)	n= xx (xx.x)
Overall a				
System Organ Class 1				
Preferred Term A				
Preferred Term B	xx.x +/- xx.x	xx.x +/- xx.x	xx.x +/- xx.x	xx.x +/- xx.x
...				
System Organ Class 2				
Preferred Term C	xx (xx.x)	xx (xx.x)	xx (xx.x)	xx (xx.x)
...				
...				

Note: Number of subjects and % of subjects are shown

a. Overall refers to any recorded AE, including AEs reported as ongoing at the time of enrollment

Run Date: ddMMMyyyy

Date of Data Extraction: ddMMMyyyy

Table 20. Continuous vs. Non-Continuous Exposure

Characteristic	Overall	Continuous Exposure (n=xx)	Non-Continuous Exposure (n=xx)
Total days of exposure, mean (SD)	xx.x (xx.x)	xx.x (xx.x)	xx.x (xx.x)
Days of longest continuous exposure, mean (SD)	xx.x (xx.x)	xx.x (xx.x)	xx.x (xx.x)

Helsinn Therapeutics (US), Inc.,  
 Protocol AC-079A501 (PROVe)

Table 21. Percent of patients with  $\geq 50\%$  reduction from baseline in % Body Surface Area of disease at 12 months ( $365 \pm 90$  days)

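### Dermatitis incidence is an objective, but AEs are summarised only as a crude percentage of patients whose follow-up differs by design, so the figure is not a risk over any stated period.

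*Protocol*

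**What the plan says.** **Objective.** The protocol synopsis and section 4 set the aim "To estimate the incidence of dermatitis in patients using Valchlor during the study observation period"; the SAP's Analysis Objectives repeat it.

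**Planned measure.** Protocol synopsis, Data Analysis: "The frequency and percentage of patients experiencing any AEs or SAEs will be summarized by system organ class and preferred MedDRA terminology". The SAP's Statistical Methods plan the same summary. Protocol 5.7.5: "The frequency and percentage of patients experiencing any on-study AEs, SAEs, or death will be summarized by system organ class and preferred MedDRA terminology". The shells of SAP Tables 18 and 19 carry the note "Note: Number of subjects and % of subjects are shown" and the footnote "Overall refers to any recorded AE, including AEs reported as ongoing at the time of enrollment". Section 5.7.5 promises separate detail on dermatitis but names no measure, and the SAP has no dermatitis table.

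**Length of follow-up.** Protocol 5.1 allows up to 2 years from consent, and staying in the study does not depend on staying on Valchlor. The synopsis adds: "Patients who enrolled and have completed 1 year of the study under the original protocol will not be re-consented under Amendment 1".

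**AE collection window.** The safety footnote to Table 1, in both documents, has AEs collected "prospectively at every visit during the study and up to 30-days post-discontinuation of Valchlor during the study". After that, new events go to the sponsor's drug safety unit only if the investigator sees a possible causal link; protocol 7.2 says the same. The SAP's Assessment Schedule text can instead be read as collecting related and unrelated events beyond 30 days as well.

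**Person-time elsewhere.** Protocol 5.7.4 divides hospitalizations and emergency visits by on-study days and uses Kaplan-Meier for hospitalization-free survival. Protocol 5.3.2 states: "Total on-study Valchlor exposure time is defined as the first day of Valchlor use to last day of Valchlor use during the observation period". No AE output uses any of these.

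**The concern.** A percentage of patients with an event is an incidence over a period only if everyone is observed for that period, or if the analysis allows for those who are not. Here two patients with the same event rate can be watched for 12 and 24 months because of when they enrolled. Under the Table 1 footnote, observation for unrelated events can also end earlier, 30 days after Valchlor stops, while the patient stays in the denominator.

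The single reported figure therefore mixes the event rate with the length of observation. Tables 18 and 19 set four concomitant-therapy groups side by side. Groups with equal AE rates but a different mix of 12- and 24-month patients, or different persistence on Valchlor, would show different percentages, and nothing in those tables would let a reader tell the two explanations apart.

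The numerator adds a second problem. The overall row includes events already ongoing at enrollment, which are prevalent and not new.

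**Working it through.** **The plan's own figure.** No AE-specific calculation is stated. The only sizing in protocol 5.5 is the margin of error of a percentage. With p = 0.5 and 95% confidence (the level is assumed, as it is not stated), 1.96 × 0.5/√n gives 5.96 points for n = 270, 6.93 for n = 200 and 9.80 for n = 100, against stated margins of 6, 7 and 10. Enrollment is 270/0.90 = 300. These reproduce, but they treat the percentage as having one fixed period.

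**Inputs to the illustration, all assumed.**
- Constant AE hazard λ of 0.1, 0.3 or 0.6 per year. The documents give no AE rate.
- 70 patients with 12 months and 200 with 24 months. The 200 echoes the projection in 5.5. The 70 is 270 − 200, a subtraction made here; the plan does not state it.
- 17.5% stop Valchlor, at times uniform over follow-up. This is the midpoint of the 15–20% in the SAP's Analysis Populations, which there describes patients who stopped and switched therapy and are left out at 12 months.
- In the stopping case, observation ends 1 month after the stop, or at the end of follow-up if that is sooner.

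**Formulas.** Risk(t) = 1 − exp(−λt). Crude without stopping = [70 × Risk(1) + 200 × Risk(2)]/270. With stopping, each Risk(T) is replaced by 0.825 × Risk(T) + 0.175 × the mean of Risk(W), with W = min(U + 1/12, T) and U uniform on 0 to T.

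**λ = 0.3, no stopping.** Risk(1) = 25.9% and Risk(2) = 45.1%. Crude = (70 × 25.9 + 200 × 45.1)/270 = 40.1%.

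**λ = 0.3, with stopping.** The mean risk among those who stop is 15.7% (12-month limit) and 26.6% (24-month limit). The 12-month stratum gives 0.825 × 25.9 + 0.175 × 15.7 = 24.1%. The 24-month stratum gives 0.825 × 45.1 + 0.175 × 26.6 = 41.9%. Crude = (70 × 24.1 + 200 × 41.9)/270 = 37.3%.

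| λ per year | 12-month risk | 24-month risk | Crude, no stopping | Crude, with stopping |
|---|---|---|---|---|
| 0.1 | 9.5% | 18.1% | 15.9% | 14.7% |
| 0.3 | 25.9% | 45.1% | 40.1% | 37.3% |
| 0.6 | 45.1% | 69.9% | 63.5% | 59.4% |

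**Check with another stopping model.** Let Valchlor stopping be exponential, with 15–20% stopped by 12 months and independent of AEs, and take a true 24-month risk of 30%. If every patient has a 24-month limit, the crude figure falls from 30.0% to 26.2–25.0%. With the assumed 70/200 mix it falls from 26.5% to 23.4–22.4%. The direction is the same; the size depends on the model.

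**The case against.** **A crude n (%) by system organ class and preferred term is conventional in a single-cohort descriptive study.** True, and it should stay. Context is planned too: person-months (Table 1A), exposure (Tables 1C and 20), AE dates in the listings, and SAE listings with and without events off Valchlor. But none of this turns the percentage into an incidence, and incidence is a stated objective.

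**The 30-day cut-off is not absolute.** A reader might infer that AE observation shrinks by rule to about a month for anyone who stops at once. The documents do not support that for all events: possibly related events remain reportable later, and the SAP's Assessment Schedule can be read as continuing collection of everything. On that second reading the effect of stopping largely disappears. What remains is 12 against 24 months, plus withdrawal and loss, and that alone leaves the percentage without a period.

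**The mechanism is weakest for dermatitis.** This stands. Dermatitis that causes stopping is already counted, later related cases are reportable, and the objective concerns patients using Valchlor. The fall with early stopping applies mainly to events not judged related.

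**The harm rests on comparisons nobody plans.** Partly right. Neither document plans an AE comparison with the pivotal trial, and Tables 18 and 19 carry no p-value footnote. The four columns are still displayed together and will be read across.

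**The numbers depend on the assumptions.** Agreed. The SAP's Table 28 uses N = 289 and gives no 12/24-month split, and if AEs cluster early the gap between the 12- and 24-month risks shrinks.

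**Conclusion.** The point holds in a limited form. The only planned AE measure is a crude percentage. Because follow-up is 12 months for some patients, up to 24 for others, and shorter with withdrawal or loss, that percentage is neither a 12- nor a 24-month risk and depends on the mix.

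At an assumed 0.3 per year the mix alone puts the crude figure at 40.1%, which is 5.0 points below the 24-month risk and 14.2 above the 12-month risk. Stopping, if it closes collection, takes off a further 2.8 points. These are illustrations of size and not estimates for this study. The lack of a fixed period does not depend on them; the fall with stopping depends on how the collection window is reconciled, and assumes that stopping is independent of the event.

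It would go too far to conclude that the planned table necessarily understates dermatitis, or that n (%) is wrong as a descriptive count. The defect is that it stands alone for an incidence objective.

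**What to change.** 1. **Reconcile the window.** Bring the Table 1 safety footnotes, protocol 7.2 and the SAP's Assessment Schedule to one stated AE collection window.
2. **Tables 18 and 19** (protocol 5.7.5 and SAP Statistical Methods). Keep n (%). Add patient-years at risk for each column, and patients with a first new on-study event per 100 patient-years. Leave events ongoing at enrollment out of this numerator.
3. **Time at risk.** Define it by the reconciled window, reopening it if Valchlor is restarted. List related events that fall after the window separately.
4. **Dermatitis and any AE.** Add cumulative incidence at 12 and 24 months from enrollment with 95% CI, using Aalen-Johansen with death as a competing event. Show newly initiating and continuing patients separately, and label the continuing group's figures as time since enrollment, because those patients were already on Valchlor.
5. **Caveat.** State that censoring at Valchlor stop, where it applies, may be informative.

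The cost is SAP wording and extra columns. Valchlor start and stop dates and AE dates are already collected, and the SAP already defines newly initiating and continuing patients. The downside is a little more analysis and wide intervals in small columns.
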